## **9.8. 24-48 hours after Starting Study Treatment (Visit 6)**

The subject will be contacted via telephone/e-mail or invited to attend the research centre approximately 24-48 hours after Visit 5 once study treatment has begun. The purpose of this visit will be to review the use of study devices and to provide any additional training required.

## **9.9. 1 Week after Starting Study Treatment (Visit 7)**

The subject will be invited to attend the research centre approximately 1 week after Visit 5. The purpose of this visit will be to review the use of study devices and to provide any additional training required.

In the UK, the visit could be done via phone / e-mail.

### **9.10. 2 Weeks after Starting Study Treatment (Visit 8)**

The subject will either be contacted via telephone/e-mail or seen in the clinic 1 week after Visit 7. The purpose of this visit would be to troubleshoot any problems. The subject is free to optimise further treatment but no active treatment optimisation will be undertaken by the study team.

### **9.11. Visits 9, 10 and 11 – 4 week, 8 week and 12 week after starting closed-loop therapy**

The subject will be invited to attend the research centre approximately 4 (Visit 9), 8 (Visit 10) and 12 (Visit 11) weeks after Visit 5. These visits could be done via telephone/e-mail. The purpose of these visits will be to review the use of study devices and data from study devices will be downloaded. The subject is free to adjust further treatment but no active treatment optimisation will be undertaken by the study team. An Actiwatch sleep monitor will be applied at Visit 10 and worn for 7 days at home. Participants will be asked to complete a sleep diary while they wear the Actiwatch and will be provided with a stamped addressed envelope to return/post the Actiwatch and sleep diary to investigators for further analysis.

### **9.12. Holter monitor application (Visit 12)**

The subject will be invited to attend the research centre within 7 days after Visit 11 to have a Holter monitor applied by the investigator. This procedure may also coincide with Visit 11. If required this visit can be done remotely by telephone once the Holter monitor has been delivered to the participant. The Holter monitor device will be collected at Visit 13, or at an agreed time and place with the investigator or returned via post/courier. Holter monitor data will be retrospectively evaluated and analysed at the end of the study. Any incidental finding will be referred by the Investigator to the clinical team and be managed as per local site policy for incidental findings.

### **9.13. End of CL treatment (Visit 13)**

The subject will be invited to attend the research centre approximately 4 weeks after visit 11. If required this visit can be done remotely by telephone. This would be the end of 4 month home study period and subjects will return to their normal diabetes care. Insulin pump and CGM device data will be downloaded. The subject will have a blood test (capillary/venous) for the HbA1c. Human factors survey assessment (Table 3) will be performed. Subjects will be asked to return the CGM and control algorithm devices, and will revert to their usual diabetes care with their usual home devices during the 1-month washout period.

## **9.14. Washout**

A minimum washout period of four weeks must be ensured between treatment periods. Duration of the wash out period has been chosen to minimise any carry over effect between the two interventions. This duration was decided pragmatically based on experience of the study team as there are no published studies investigating an optimal washout period for closed-loop studies. The subject may continue to use the study CGM and study insulin pump during the washout period if he or she wishes. Otherwise the subject will continue to use their usual diabetes care with their usual home devices during the washout period. Then the subject will cross over to alternative intervention.

## **9.15. Control therapy (Visit 14)**

The order of Visit 5 and Visit 14 will be in random order. Visit 14 is similar to Visit 5 except that in Visit 14 there is no closed-loop insulin training and application, and subjects will initiate sensor augmented insulin pump therapy. If required this visit can be done remotely by telephone. Subjects will follow usual treatment guidelines for driving, exercise, hyperglycaemia and hypoglycaemia.

## **9.16. Visits 15, 16 and 17 – 4 week, 8 week and 12 week after starting sensor augmented pump treatment**

The subject will be invited to attend the research centre approximately 4 (Visit 15), 8 (Visit 16) and 12 (Visit 17) weeks after Visit 14. If required these visits can be done remotely via telephone/e-mail. The purpose of this visit will be to review the use of study devices and data from study devices will be downloaded. The subject is free to adjust further treatment but no active treatment optimisation will be undertaken by the study team. At Visit 16, an Actiwatch sleep monitor will be applied and worn for 7 days at home. Participants will be asked to complete a sleep diary and will be provided with a stamped addressed envelope to return/post the Actiwatch to investigators for further analysis.

## **9.17. Holter monitor application (Visit 18)**

The subject will be invited to attend the research centre within 14 days after Visit 17 to have a Holter monitor applied by the investigator. If required this visit can be done remotely by telephone once the Holter monitor has been delivered to the participant. This procedure may also coincide with Visit 17. The Holter monitor device will be collected at Visit 19, or at an agreed time and place with the investigator or returned via post/courier. Holter monitor data will be retrospectively evaluated and analysed at the end of the study. Any incidental finding will be referred by the Investigator to the clinical team, to be managed as per local site policy for incidental findings.

## **9.18. End of control treatment (Visit 19)**

The subject will be invited to attend the research centre approximately 4 weeks after Visit 17. If required this visit can be done remotely by telephone. This would be the end of the study period and subjects will return to their normal diabetes care. Insulin pump will be downloaded. The subject will have a blood test (capillary/venous) for the HbA1c. A human factors survey assessment (Table 3) will be performed. Participants will be invited to a focus group for investigators to gather feedback and reactions to the closed-loop system, the clinical trial, and quality of life changes.

## **9.19. Participant withdrawal criteria**

The following pre-randomisation withdrawal criteria will apply:

1. Subject is unable to demonstrate safe use of study insulin pump and / or CGM during run-in period as judged by the investigator
2. Subject fails to demonstrate compliance as mentioned in section 9.5 with study insulin pump and / or CGM during run-in period

The following pre- and post-randomisation withdrawal criteria will apply:

3. Subjects may terminate participation in the study at any time without necessarily giving a reason and without any personal disadvantage
4. Significant protocol violation or non-compliance
5. Any severe hypoglycaemia event related to use of the closed-loop system
6. Two severe hypoglycaemia events unrelated to the use of the closed-loop system
7. DKA unrelated to infusion site failure and related to the use of the closed-loop system
8. Decision by the investigator or the sponsor that termination is in the subject's best medical interest

9. Allergic reaction to insulin
10. Severe allergic reaction to adhesive surface of infusion set or glucose sensor

Subjects who are withdrawn for reasons stated in (4) to (10) will be invited to provide a blood sample at the end of the planned study intervention for the assessment of HbA1c.

## **9.20. Study Stopping Criteria**

The study may be stopped if three consecutive participants withdraw on safety grounds or on the advice of an independent Data Safety and Monitoring Board (DSMB).

## **9.21. Support telephone line**

There will be a 24-hour telephone helpline to the research team for subjects in case of any technical device or problems related to diabetes management such as hypo- or hyperglycaemia.

## **9.22. Subject reimbursement**

The study will provide the CGM device, insulin pump, closed-loop components, related consumables, and glucose test strips. A recompense payment to participants will be paid to reflect local practice. The amount paid will be specified in the participant information sheet and REC application form. Reasonable travel expenses will also be reimbursed. After completing the study, subjects will not keep the study devices. They will revert to their conventional insulin pump therapy.

# **10. Endpoints**

## **10.1. Efficacy endpoints**

### **10.1.1. Primary efficacy endpoint**

The primary outcome is the time spent in the target glucose range from 3.9 to 10.0 mmol/l (70 to 180mg/dl) throughout the 16 week study periods based on continuous glucose monitoring (CGM).

### **10.1.2. Secondary efficacy endpoints**

Key secondary outcomes include:

- Time spent above target glucose (10.0 mmol/l) (180 mg/dl)
- Average of glucose levels
- HbA1c at 16 weeks
- Time spent below target glucose (3.9mmol/l) (70mg/dl)

Other secondary endpoints

- standard deviation and coefficient of variation of glucose levels
- The time with glucose levels <3.5 mmol/l (63mg/dl), and <3.0 mmol/l (54mg/dl)
- The time with glucose levels in the significant hyperglycaemia (glucose levels >16.7 mmol/l) (300mg/dl)
- Total, basal and bolus insulin dose

Glucose endpoints will be based on sensor glucose.

## **10.2. Safety evaluation**

Safety evaluation will comprise number of episodes of severe hypoglycaemia as well as the number of subjects experiencing severe hypoglycaemia, severe hyperglycaemia (fingerprick glucose >16.7 mmol/l) (>300mg/dl) and plasma ketones >0.6mmol/l), diabetic ketoacidosis, and other adverse events.

All subjects including those who withdraw will be included in the safety evaluation.

## **10.3. Utility evaluation**

Utility evaluation is the frequency and duration of use of the closed-loop system at home.

## **10.4. Human factors evaluation**

Cognitive, emotional, and behavioural characteristics of participating subjects and family members and their response to the closed-loop system and clinical trial will be assessed using validated surveys and focus groups.

## **10.5. Cardiac arrhythmia analysis**

Holter monitor data at the fourth month in the two treatment groups will be retrospectively evaluated by a cardiologist masked to other study data at the end of the study. Any incidental finding will be referred by the Investigator to the clinical team and be managed as per local incidental findings site policy.

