End of study assessments	A blood sample (capillary/venous) will be taken for measurement of HbA1c. Human factor assessment will be performed to understand expectations, attitudes, and behaviours that influence the uptake and response to using a closed-loop system. The human factor assessments include both quantitative and qualitative methods which have been tested in adults in the targeted age range.
Actiwatch application at 2-month of each study period	Subjects will wear an Actiwatch for 7 days for objective sleep quality assessment.
Holter monitor application during the last month of each study period	Subjects will wear a Holter monitor for 5-7 days for retrospective analysis of cardiac rhythm during each study period. Holter monitor data will be analysed at the end of the study. Any incidental finding will be referred by the Investigator to the clinical team and be managed as per local site policy.
Procedures for safety monitoring during trial	
Standard operating procedures for monitoring and reporting of all adverse events and adverse device events will be in place, including serious adverse events (SAE), serious adverse device effects (SADE) and specific adverse events (AE) such as severe hypoglycaemia.
 
A Data Safety and Monitoring Board (DSMB) will be informed of all serious adverse events and any unanticipated adverse device/method effects that occur during the study and will review compiled adverse event data at periodic intervals.

Criteria for withdrawal of patients on safety grounds	
A subject may terminate participation in the study at any time without necessarily giving a reason and without any personal disadvantage. An investigator can stop the participation of a subject after consideration of the benefit/risk ratio. Possible reasons are:
 
 
• Serious adverse events
 
• Significant protocol violation or non-compliance
 
• Failure to satisfy competency assessment
 
• Decision by the investigator, or the sponsor, that termination is in the subject's best medical interest
 
• Allergic reaction to insulin
 
• Technical grounds (e.g. subject relocates)
 

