### **11.3.8. Holter monitor**

Potential risks and adverse device effects associated with Holter monitor:

- Slight discomfort at the time of electrode adhesives placement (rare)
- Mild skin irritation to electrode adhesives (rare)

If an incidental finding is found during analysis of the Holter monitor data at the end of the study period, this will be referred by the Investigator to the clinical team, to be managed as per local site policy.

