## **12.1.5. Holter monitor**

At least 5 days of Holter monitor data will be collected during the fourth month in the two treatment groups and analysed at the end of the study period. Any incidental finding will be referred by the Investigator to the clinical team and be managed as per local site policy.

An incidental finding may be defined as 'a finding that has potential health or reproductive importance, unknown to the participant, which is discovered unexpectedly in the course of conducting research, but is unrelated to the purpose and beyond the aims of the study'. This study will adopt the following framework for handling incidental findings:

- To respect the research participant's right to know or, alternatively, their right not to know about incidental findings. Explicit consent must have always been given by the participant for incidental findings to be returned.
- Incidental findings should only be returned where they are of significant clinical importance.
- Incidental findings should be clinically and analytically validated before being returned to participants by their treating clinician.
- Feedback to individual participants should be conducted by a trained professional.

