#### **14.2.3. Cardiac Arrhythmia Analysis**

Holter monitor data at the fourth month in the two treatment groups will be analysed at the end of the study period. Arrhythmic events analysed will include atrial fibrillation, atrial ectopic beats, bradycardia, ventricular premature beats, complex ventricular premature beats, non-sustained ventricular tachycardia and measures of heart rate variability and QT interval. All identified arrhythmic events will be manually verified for accuracy.

Investigators will be blinded to glucose values during arrhythmia analysis. The frequency of arrhythmic events during periods of hypoglycaemia (sensor glucose  $\leq 3.9$  mmol/L and 3.0 mmol/L), will be compared to the frequency of arrhythmic events during normoglycaemia (3.9-10 mmol/L) within each study arm. Analyses will be calculated for daytime and night-time periods to take into account diurnal variation. Any incidental finding will be referred by the Investigator to the clinical team and be managed as per local site policy.

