225 **7.9 Sleep Analyses**

226 The Pittsburgh Sleep Quality Index (PSQI) and actigraphy data will be used to calculate mean
227 total sleep quality score, sleep duration, time in bed, sleep disturbance (including wake after
228 sleep onset and number of awakenings), latency, efficiency, quality, and daytime dysfunction.

229 Sleep will be automatically scored by Actiware software using previously described and
230 validated algorithms. Sleep duration will be calculated as the sum of all epochs scored as sleep
231 during the time in bed. Variability across nights in a participant's sleep duration will be
232 summarised using the coefficient of variation. Sleep data will be averaged across nights in each
233 participant for each study period. The analysis will be conducted by [name]

234 **7.10 Holter Data Analyses**

235 Holter monitor data at the fourth month in the two treatment groups will be analysed at the end
236 of the study. Arrhythmic events analysed will include atrial fibrillation, atrial ectopic beats,
237 bradycardia, ventricular premature beats, complex ventricular premature beats, non-sustained
238 ventricular tachycardia and measures of heart rate variability and QT interval. All identified
239 arrhythmic events will be manually verified for accuracy.

240 Investigators will be masked to glucose values during arrhythmia analysis. The frequency of
241 arrhythmic events during periods of hypoglycaemia (sensor glucose ≤ 3.9 mmol/L and 3.0
242 mmol/L), will be compared to the frequency of arrhythmic events during normoglycaemia (3.9-
243 10 mmol/L) within each study arm. Analyses will be calculated for daytime and night-time
244 periods to take into account diurnal variation. Any incidental finding will be referred by the
245 Investigator to the clinical team and be managed as per local site policy.

246

247 **8. Safety Analyses**

248 All safety outcomes will be tabulated by participant for all events from enrollment to the final
249 study visit.

250 **8.1 Definitions**

251 Reportable adverse events for this protocol include any untoward medical occurrence,
252 unintended disease or injury, or untoward clinical signs (including abnormal laboratory findings)
253 in a subject who has received an investigational device, whether or not related to the
254 investigational medical device. These include severe hypoglycemia (SH) and diabetic
255 ketoacidosis (DKA).

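### The Holter wording lets a period-1 recording stay unread until the participant has finished period 2, about 21 to 23 weeks or more, so referral of a silent arrhythmia can be delayed that long

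*Protocol*

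**What the plan says.** Each participant wears a Holter monitor in the last month of each arm. Eight places say when the recordings are read.

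Five set the read at study end:
- Protocol 2 (Synopsis): "Holter monitor data will be analysed at the end of the study".
- Protocol 9.12 (Visit 12, closed-loop arm) and 9.17 (Visit 18, control arm), in the same words: "Holter monitor data will be retrospectively evaluated and analysed at the end of the study".
- Protocol 10.5, which also names the reader: "will be retrospectively evaluated by a cardiologist masked to other study data at the end of the study".
- SAP 7.10: "Holter monitor data at the fourth month in the two treatment groups will be analysed at the end", with the sentence completed on the next line by the words for study end.

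Three use a different phrase:
- Protocol 11.3.8: "If an incidental finding is found during analysis of the Holter monitor data at the end of the study period".
- Protocol 12.1.5: "in the two treatment groups and analysed at the end of the study period".
- Protocol 14.2.3: "Holter monitor data at the fourth month in the two treatment groups will be analysed at the end of the study period".

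All eight add that an incidental finding goes to the clinical team, and none gives a turnaround time. On device return, Protocol 9.12 says: "The Holter monitor device will be collected at Visit 13, or at an agreed time and place with the investigator or returned via post/courier". Tables 1 and 2, the text for Visits 13, 14 and 19, the washout text in 9.14 and the list of data for the DSMB in SAP 11 contain no Holter review.

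**The concern.** A finding can be referred only after someone has looked at the recording. Under the study-end wording, the period-1 recording may be back with the investigators at about week 16 and still be unopened while the participant goes through washout and another 16 weeks of treatment.

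The protocol itself gives the reason to care. Its Background says that hypoglycaemia unawareness is common in older people with type 1 diabetes and that severe hypoglycaemia predisposes to arrhythmia and cardiovascular death. The rhythms listed in 14.2.3 include atrial fibrillation, bradycardia and non-sustained ventricular tachycardia.

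Two safeguards exist: the 12-lead ECG at recruitment, with referral (12.1.4), and the asking about adverse events at each visit (11.2.2). They leave one gap, the silent arrhythmia that is intermittent or that arose after the baseline ECG. Several days of Holter recording can show such an arrhythmia. What is at stake is how soon the participant's clinical team hears of it.

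**Working it through.** **Which wording governs.** The three end-of-period places are ambiguous. Protocol 9.1 calls each four-month arm a study period, which would put the read at the end of each arm. Protocol 9.18 uses the singular phrase for Visit 19, the last visit in the closed-loop-first order, which would put it at the end of participation. Three facts favour the later reading:
- The visit text for both recordings (9.12 and 9.17) says study end.
- The synopsis row calls the arms study periods and then places the read at the end of the study, so it separates the two ideas.
- SAP 7.10 repeats the 14.2.3 sentence but ends it at the study, not the study period.

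This is the weight of the text and does not prove intent.

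**Inputs**, in weeks from the start of period 1:
- Visit 11 or 17 at week 12 (9.11, 9.16).
- Monitor applied at that visit or up to 14 days later (Tables 1 and 2, 9.17). Section 9.12 allows only 7 days for the closed-loop recording.
- Wear of 5 to 7 days (Synopsis, Table 1). Table 2 says 5 days.
- Period 1 ends at week 16, washout lasts 4 weeks, and period 2 lasts 16 weeks.

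**End of the period-1 recording**
- Earliest: 12 + 5/7 = 12.7.
- Latest: 12 + 2 + 1 = 15.0.
- Closed-loop first under 9.12: latest 12 + 1 + 1 = 14.0.
- Control first under Table 2: latest 12 + 2 + 5/7 = 14.7.

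**Wait until the read**
- If the phrase means each arm (week 16): 16 − 15.0 = 1.0 to 16 − 12.7 = 3.3 weeks. This raises no problem.
- If study end means the participant's own completion (16 + 4 + 16 = week 36): 36 − 15.0 = 21.0 to 36 − 12.7 = 23.3 weeks. For closed-loop first under 9.12 it is 36 − 14.0 = 22.0 to 23.3 weeks. For control first under Table 2 it is 36 − 14.7 = 21.3 to 23.3 weeks. Of this, 36 − 16 = 20 weeks fall after planned device collection.
- If study end means the end of the trial, the wait is longer. As an illustration for the first participant, take the planned dates in Protocol 20 (entry in Q2 2019, last completion in Q4 2020) and assume 3 to 10 weeks from Visit 1 to period 1. The shortest wait runs from 30 June 2019 to 1 October 2020: 459/7 − 10 − 15.0 = 40.6 weeks. The longest runs from 1 April 2019 to 31 December 2020: 640/7 − 3 − 12.7 = 75.7 weeks.

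**Gain from reading on return.** The documents give no reading time, so I assume 1 to 4 weeks.
- Device back at week 16: read by week 17 to 20, which is 36 − 20 = 16 to 36 − 17 = 19 weeks sooner than week 36.
- Device back 8 weeks late, at week 24 (assumed): read by week 25 to 28, which is 36 − 28 = 8 to 36 − 25 = 11 weeks sooner.

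**The case against.** The strongest defence is that this is an openly stated design choice. The Holter serves a research objective (5.5), it is not in the safety evaluation of 10.2, and a single masked read at study end is orderly. Three places permit an end-of-arm reading, and nothing forbids an earlier look. Consent pages and local site policy, which are outside the review copy, may already provide for one. No rate of actionable silent arrhythmia is given, so 21 to 23 weeks measures delay and not risk. All of this stands and limits the claim. It does not remove the lack of a clear rule, or the fact that referral has to wait for the read.

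A second defence is scientific. Acting on a period-1 read can change cardiac treatment before the period-2 recording, whereas study-end reading avoids that. The cost is real but small. Randomised order largely balances such changes across treatments, the comparison by glucose level in 14.2.3 is made within each arm, and the primary endpoint is a CGM measure. The balance is not exact if the treatments differ in arrhythmia frequency, so the changes should be recorded and examined.

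The definition in 12.1.5 is a minor matter. It describes an incidental finding as outside the aims of the study, although arrhythmia is one of those aims. A reader might infer that arrhythmias are excluded from referral. The documents do not support that, because the definition is permissive and every Holter section repeats the intent to refer.

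**Conclusion.** The point holds as a cheap improvement to participant safety. Five of the eight places set the read at study end, three are open to either meaning, and none expressly requires a read before crossover. Under the study-end wording the period-1 recording may wait about 21 to 23 weeks, or longer if trial end is meant. This rests on the scheduled visit times, the stated wear times and a four-week washout.

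Stronger conclusions are tempting but unsupported. A reader might infer that every period-1 recording must stay sealed until study end, but the plan permits an earlier read and does not demand one. A reader might infer that participants will be harmed, but no event rate is available and none is estimated. A reader might infer that an earlier read would change period-2 allocation or the primary result, but nothing in the documents indicates the first, and the primary analysis does not use Holter data.

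**What to change.** Use one timing rule in all eight places (Protocol 2, 9.12, 9.17, 10.5, 11.3.8, 12.1.5, 14.2.3 and SAP 7.10):
- The same masked cardiologist reads each recording when it is returned. The aim is to read the period-1 recording during the existing washout.
- Crossover is not held up by a late device or a pending read. Slack is small, because 9.14 sets a minimum washout of four weeks and 9.1 puts the two periods within four weeks of each other.
- Clinically important arrhythmias are referred whether or not they are study outcomes, subject to the consent given. Clinical handling stays with local policy.
- The statistical arrhythmia comparison stays at study end.

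The change needs no extra visit, recording or reader, and masking to glucose is kept because the read uses no CGM data. It has three costs:
- Reading and manual verification become rolling instead of batched, for about 36 × 2 = 72 recordings. This is not a ceiling: Protocol 3, 7.1 and 14.6 treat 36 as the target for completers, with 40 to 42 recruited, so drop-outs can add a few.
- The consent wording must be checked, since 12.1.5 makes explicit consent a condition of returning findings.
- Cardiac treatment changes made before the period-2 recording must be dated and examined in a sensitivity analysis of the rhythm, QT and heart-rate-variability outcomes.
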